1 PROTOCOL SUMMARY

1.1 SYNOPSIS

Title:	Food Additive Removal Diet for Pediatric Eosinophilic Esophagitis (FREE)
Study Description:	Prospective, pragmatic standard of care clinical trial comparing dietary therapies of dairy elimination diet (DED) to dairy + food additive elimination diet (FREE) in children with eosinophilic esophagitis.
Objectives:	
Primary Objective: To compare histologic outcomes (eosinophils per high power field: eos/hpf) of dairy elimination diet (DED) to dairy + food additive elimination diet (FREE) in children with eosinophilic esophagitis.
 
Secondary Objective: To compare endoscopic outcomes (Eosinophilic Esophagitis Endoscopic Reference scores: EREFs) of dairy elimination diet (DED) to dairy + food additive elimination diet (FREE) in children with eosinophilic esophagitis
 
Tertiary Objectives: To compare symptomatic (Pediatric Eosinophilic Esophagitis Symptom Severity Module v2.0: PEES) and quality of life (Peds-QL EoE Module 1) outcomes of dairy elimination diet (DED) to dairy + food additive elimination diet (FREE) in children with eosinophilic esophagitis

Endpoints:	
Primary Endpoint: (1) Histologic change differences of maximum eos/hpf baseline vs 12 week endoscopy
 
Secondary Endpoint: (1) EREFs: Eosinophilic Esophagitis Endoscopic Reference Score baseline vs 12 weeks
 
Tertiary Endpoints: (1) Patient Reported Outcomes (Pediatric Eosinophilic Esophagitis Symptom Severity Module (PEES) baseline vs 12 weeks, (2) quality of life (PedsQL-EoE)¹ baseline vs 12 weeks

Study Population:	We will plan to enroll 72 patients. Based on histologic primary outcome efficacy estimates of DED (50%) compared to FREE (estimated 70%) and a sample size of 36 enrolled patients per group (72 total) with 88% power, we will be able to demonstrate a detectable difference of 30% among two

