1.2 SCHEMA

1.3 SCHEDULE OF ACTIVITIES

Procedures	Screening Day -7 to 1	Enrollment/Baseline Visit 1, Day 1	Study Visit 2 (FUP Call) Day 7 (week 1) +/-2 days	Study Visit 3 (FUP Call) Day 14 (week 2) +/- 2 days	Study Visit 4 (FUP Call) Day 21 (week 3) +/-2 days	Study Visit 5 (FUP Call) Day 28(week 4) +/-2 days	Study Visit 6(FUP Call) Day 35 (week 5) +/-2 days	Study Visit 7 (FUP Call) Day 42 (week 6) +/-2 days	Study Visit 8 (FUP Call) Day 49 (week 7) +/-2 days	Study Visit 9 Day 56 (week 8) +/-14 days	Study Visit 10 Day 63 (week 9) +/-14	Study Visit 11 Day 70 (week 10) +/-14	Study Visit 12 Day 77 (week 11) +/-14	Study Visit 13 Day 84 (week 12) +/-14
Informed consent	X													
Review Inclusion/Exclusion Criteria	X													
Medical History	X													
Demographics		X												
Pathologist Questionnaire / Peak Eosinophils per high power field (Eos/hpf)	X													X
Randomization		X												
Personal Information		X												
Height and Weight		X												X
Eosinophilic Esophagitis Endoscopic Reference Score (EREF)		X												X
Diet Education		X												
Dietician Follow Up Calls			X			X			X				X	
Three-day Diet Diary		X												X
Quality of Life (PedsQL EoE)(Parent & Child)		X				X*				X*				X*
Pediatric Eosinophilic Esophagitis Symptom Severity Module (PEESS)(Parent & Child)		X				X*				X*				X*
Adverse Event Reporting (Safety Q)		X				X*				X*				X*

Procedures	Screening Day -7 to 1	Enrollment/Baseline Visit 1, Day 1	Study Visit 2 (FUP Call) Day 7 (week 1) +/-2 days	Study Visit 3 (FUP Call) Day 14 (week 2) +/- 2 days	Study Visit 4 (FUP Call) Day 21 (week 3) +/-2 days	Study Visit 5 (FUP Call) Day 28(week 4) +/-2 days	Study Visit 6(FUP Call) Day 35 (week 5) +/-2 days	Study Visit 7 (FUP Call) Day 42 (week 6) +/-2 days	Study Visit 8 (FUP Call) Day 49 (week 7) +/-2 days	Study Visit 9 Day 56 (week 8) +/-14 days	Study Visit 10 Day 63 (week 9) +/-14	Study Visit 11 Day 70 (week 10) +/-14	Study Visit 12 Day 77 (week 11) +/-14	Study Visit 13 Day 84 (week 12) +/-14
Concomitant medication review	X	X		X	X		X	X		X			X	X
Coordinator Call				X	X		X	X		X	X		X	
Payment to Part. for Completed Visit		X				X				X				X

* REDCap survey – completed by participant/parent

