3 OBJECTIVES AND ENDPOINTS

OBJECTIVES	ENDPOINTS	JUSTIFICATION FOR ENDPOINTS
Primary		
To compare histologic outcomes of DED and FREE among children with eosinophilic esophagitis	Maximum eos/hpf (primary)	Eosinophils are a biomarker of inflammation. Current diagnostic criteria specify ≥ 15 eos/hpf. A reduction in eos/hpf should correlate with a reduction in symptoms. A successful treatment outcome is < 15 eos/hpf.
Secondary		
To compare endoscopic outcomes of DED and FREE among children with eosinophilic esophagitis	Eosinophilic Esophagitis Endoscopic Reference Score (EREFs)(secondary)	Includes additional eosinophil morphology and associated histopathologic features (e.g. degranulation, microabscesses, superficial layering, basal zone hyperplasia)
Tertiary/Exploratory		
To compare quality of life and patient reported outcomes of DED and FREE among children with eosinophilic esophagitis	PedsQL-EoE (tertiary) Pediatric Eosinophilic Esophagitis Symptom Severity Module (PEESS) (tertiary)	Determines the impact of DED and FREE on QOL and symptom severity, which is not routinely assessed.

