5 STUDY POPULATION

5.1 INCLUSION CRITERIA

Inclusion criteria

To be eligible to participate in this study, all of the following criteria must be met:

1. An Institutional Review Board (IRB) approved written Parental Permission form is signed and dated by the parent or legal representative/caregiver.
2. An Institutional Review Board (IRB) approved written Assent form is signed and dated by the participant.
3. The participant/parent(s) or legal representative(s)/caregiver(s) are considered reliable and capable of adhering to the protocol call schedule and dietary requirements.
4. The participant is ≥ 2 years to 18 years of age.
5. The participant has isolated esophageal eosinophilia (>15 eos/hpf).
6. The biopsy used to diagnose eosinophilic esophagitis was taken no more than 12 weeks prior to the date of enrollment.
7. The family has access to the internet to complete weekly surveys and to a telephone to complete weekly follow up calls.

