5.3 STRATEGIES FOR RECRUITMENT AND RETENTION

Providers at participating sites will be educated on the study protocol. Local pathologists will notify study coordinators of patient eligibility. Samples from standard of care biopsies will be batch shipped to the lead site for analysis by the central pathologist. The samples will be identified by the study ID only. Only the originating site can link the codes to the patient.

M. Collin's recommended criteria for the diagnosis of eosinophilic esophagitis (EE) will be used to evaluate the esophageal biopsies.²⁴ The central pathologist, who has extensive experience in the diagnosis of EE will review all biopsies, blind to patient's dietary status. The grading and staging of EE will be based on Collin's criteria, especially to be focused on eosinophilic inflammation, epithelial basal zone changes, eosinophilic abscess, and lamina propria fibrosis. Samples will be returned to the originating sites after central pathology review.

Patients (or in the case of children, the pediatric patient and their parent/legal guardian) will be approached for participation after a clinical assessment has been performed by a GI provider. Study procedures will be performed after obtaining proper consent and/or child assent. In addition, the clinic schedule will be reviewed each week for potential participants. If possible, patients or families will be contacted ahead of time to determine their interest in the study, should they qualify for participation.

Participants will be paid the following: Baseline Visit \$25.00 + 2 weeks of surveys X \$25 + Final Visit \$50.00 = \$125.00 per participant. The telephone follow up and the participant questionnaires must be completed at each designated visit to receive payment. Gift cards will be mailed to participants upon the completion of each eligible visit.

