6.2 MEASURES TO MINIMIZE BIAS: RANDOMIZATION

A randomization table will be generated for each site via *randomization.com* and will be used for assigning eligible participants to a treatment regimen.

To enroll a participant (Visit 1), the investigator (or designee) will assign each participant a 5-digit number which serves as the participant identifier throughout the study.

To randomize a participant (Visit 1), the investigator (or designee) will notify the lead site that a participant has been enrolled. The lead site will randomize the patient.

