9 STATISTICAL CONSIDERATIONS

9.1 STATISTICAL HYPOTHESES

Based on histologic primary outcome efficacy estimates DED without PPI therapy (50%) compared to FREE (estimated 70%) a sample size of 36 enrolled patients per group (72 total) with 88% power, we will be able to demonstrate a detectable difference between the three groups, we assume the standard deviation for both groups to be 30%. We hypothesize that changes in primary and secondary endpoints for FREE participants will be superior to DED.

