9.4 STATISTICAL ANALYSES

Primary analyses will assess effectiveness endpoints, including eos/hpf and EREFs. Efficacy variables will be summarized descriptively and compared between treatment groups.

Secondary analyses include descriptive statistics of the patient population (patient demographics, clinical characteristics, and comorbid conditions), concomitant medications used in this patient population and changes to these treatments.

Categorical variables will be described using frequencies and percentages while continuous variables will be described using means, standard deviations, medians, and inter-quartile ranges.

Independent sample t-tests will be conducted to compare outcomes between groups.

Additional analysis plans may be developed based on clinical considerations.

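### The unadjusted t-test on change in eos/hpf is valid, but ANCOVA on the baseline values already collected would usually be more precise, by an amount the documents cannot fix

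*Combined protocol and SAP*

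**What the plan says.** Section 9.4 states: "Independent sample t-tests will be conducted to compare outcomes between groups". It names no regression model, baseline covariate or site term. It leaves room for further analysis plans but specifies none.

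The synopsis (section 1.1) defines the primary endpoint as "Histologic change differences of maximum eos/hpf baseline vs 12 week endoscopy", and section 9.1 frames its hypothesis in terms of changes in the endpoints. The table in section 3 lists only "Maximum eos/hpf (primary").

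The baseline data exist. The schedule in section 1.3 has a row "Pathologist Questionnaire / Peak Eosinophils per high power field (Eos/hpf") marked at screening and week 12. EREFs, PedsQL-EoE and PEESS are all marked at baseline and week 12. Section 5.3 adds: "Samples from standard of care biopsies will be batch shipped to the lead site for analysis by the central pathologist".

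On allocation, section 6.2 says: "A randomization table will be generated for each site". It mentions neither blocking nor the number of sites. For sample size, section 9.1 takes 50% against 70% with 36 per group and 88% power, and says "we assume the standard deviation for both groups to be 30" percent.

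**The concern.** If baseline and week-12 counts are only weakly related, subtracting baseline adds noise to the outcome. ANCOVA instead estimates how much of baseline to remove.

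A weak relation is plausible here. Entry is cut off at about 15 eos/hpf, which narrows the baseline range. Section 5.1 also allows an old baseline: "The biopsy used to diagnose eosinophilic esophagitis was taken no more than 12 weeks prior to the date of enrollment". With 12 weeks of diet and a 14-day window, that biopsy can be 12 + 12 + 2 = 26 weeks old at the final endoscopy.

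Section 9.2 says the sample size was set by how many patients were available, and the synopsis expects 20% drop-out. Precision is therefore hard to buy with more children, while the baseline values cost nothing extra.

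**Working it through.** **Inputs.** 36 per group, difference 70 − 50 = 20 and SD 30 come from section 9.1. The 20% drop-out comes from section 1.1 and gives 36 × 0.8 = 28.8, or about 29 per group. Alpha, r and the SD ratio are not stated and are assumed. The 20/30 scale is a percentage, not eos/hpf. If 50 and 70 are response rates, only the ranking of methods carries over.

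**1. The plan's own figure.** SE = 30 × √(2/36) = 7.07, and 20/7.07 = 2.83. By normal approximation, power is 88.2% at one-sided 0.05 and 80.7% at two-sided 0.05. So 88% reproduces as an unadjusted comparison of two means at one-sided 0.05. Everything below uses two-sided 0.05 and the noncentral t, which gives 79.7% at 36 per group and 70.4% at 29.

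**2. Variances.** Let s0 and s1 be the baseline and week-12 SDs.
- Change score: s0² + s1² − 2·r·s0·s1
- ANCOVA: s1²(1 − r²)
- Difference: (s0 − r·s1)², which is never negative and is zero only when r = s0/s1

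With equal SDs the ratio of ANCOVA to change is (1 + r)/2.

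**3. Power when 30 is the SD of change and SDs are equal.** Residual SD = 30 × √((1 + r)/2), with 2n − 3 degrees of freedom for ANCOVA.

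| | r = 0 | 0.3 | 0.5 | 0.7 |
|---|---|---|---|---|
| Residual SD | 21.2 | 24.2 | 26.0 | 27.7 |
| Change t-test, n = 36 | 79.7% | 79.7% | 79.7% | 79.7% |
| ANCOVA, n = 36 | 97.6% | 93.3% | 89.6% | 85.7% |
| Change t-test, n = 29 | 70.4% | 70.4% | 70.4% | 70.4% |
| ANCOVA, n = 29 | 94.1% | 87.1% | 82.1% | 77.2% |

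Chance imbalance in baseline multiplies the ANCOVA variance by 1 + 1/(2n − 4). At 36 per group that takes off at most 0.5 points.

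**4. Baseline SD half the week-12 SD.** The variance ratio is (1 − r²)/(1.25 − r) = 0.80, 0.96, 1.00 and 0.93 at the same four r. With SD of change 30 and 36 per group, ANCOVA has 87.7, 81.3, 79.6 and 82.5% against 79.7%. The gain is close to nil for r around 0.3 to 0.5.

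**5. Against a t-test on the week-12 count.** The ratio is 1 − r². If 30 is the week-12 SD, ANCOVA has 79.6, 83.2, 89.6 and 97.4% against 79.7%. With a useless baseline (r = 0) and chance imbalance included, power falls from 79.7% to 79.1% at 36 per group and from 70.4% to 69.5% at 29. Break-even is at |r| of about 0.12 to 0.13.

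**6. Adding site.** With p covariates (baseline plus sites minus 1), no site effect and arms not balanced within site, the variance factor is 1 + p/(2n − 3 − p). For 12 assumed unpooled sites p = 12, giving 1 + 12/57 = 1.21 at 36 per group and 1 + 12/43 = 1.28 at 29.
- r = 0.3, week-12 SD 30, 36 per group: 75.5%, against 79.7% for the week-12 t-test.
- r = 0.7, SD of change 30, 29 per group: 66.3%, against 70.4% for the change t-test.
- If arms balance within site, only degrees of freedom are lost: 79.4% at r = 0 and 36 per group.

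**7. Skewed counts.** A simulation took 50% against 70% remission, 36 per group, log-normal baseline cut at 15, remitters uniform on 0 to 14 and non-remitters at 15 or more. The four settings implied r from 0.09 to 0.43. All of these are assumptions.

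| | Setting 1 | 2 | 3 | 4 |
|---|---|---|---|---|
| Change t-test | 22.6% | 12.4% | 27.8% | 18.7% |
| Week-12 t-test | 31.6% | 21.9% | 30.3% | 23.2% |
| ANCOVA | 31.1% | 22.2% | 33.0% | 26.1% |

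ANCOVA beats change by 8.5, 9.8, 5.2 and 7.4 points. It is level with the week-12 t-test in the first two settings and ahead by 2.7 and 2.9 points in the others. Rejection under the null was 4.3 to 5.3% for all three methods.

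**The case against.** Randomization justifies the unadjusted test, so nothing here is an error. The size of the gain rests on r, alpha, the SD ratio and a count distribution that the documents do not supply. At 58 to 72 children the large-sample guarantee is only approximate. All of this stands, and it is why no single gain is claimed.

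A reader might infer from section 3 that the plan leaves open whether change or the week-12 count is tested. The documents lean clearly the other way: the synopsis and section 9.1 both speak of change, and the section 3 table names the measured variable. The relevant comparison is therefore with the change-score t-test, where ANCOVA gains most at low r.

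A reader might also infer that randomizing by site obliges the analysis to include site. Section 6.2 describes a table per site but no blocks, so balance within site cannot be assumed. Remote participants (sections 10.1.1.1 and 10.1.4) also have no obvious site. Step 6 shows that many small sites can cost more than baseline adjustment gains. In the skewed simulation with 12 unpooled sites, the advantage over change shrank to about 1 to 7 points, and the week-12 t-test did better in three of four settings.

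**Conclusion.** The point holds as a gain in precision, not as a fault in the test. Against the change-score t-test, baseline-adjusted ANCOVA is at least as precise in large samples under 1:1 allocation. On the illustrative scale, with equal SDs and 36 per group, the gain runs from 6.0 power points at r = 0.7 (85.7 − 79.7) to 17.9 at r = 0 (97.6 − 79.7). It is close to zero when r is near the ratio of baseline to week-12 SD. The most that a useless baseline costs against a week-12 t-test is under one point.

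The documents do not support reading this as a remedy for the trial's power. In the skewed-count simulation every method stayed between 12 and 33%, and the percentage-scale figures do not translate into eos/hpf.

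**What to change.** In section 9.4, make the primary analysis an ANCOVA of week-12 maximum eos/hpf on arm and baseline maximum eos/hpf. Take both values from the central pathologist's read, not the local eligibility read. Report the adjusted mean difference with a 95% CI. With baseline in the model, using change or the week-12 value as the outcome gives the same treatment estimate, so the wording of the endpoint no longer matters.

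Use the same form, each with its own baseline, for EREFs, PedsQL-EoE and PEESS. Keep the change-score t-test as a sensitivity analysis.

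State whether the per-site tables were blocked. Only if they were, add site as a term, with small sites (and remote participants) pooled by a rule fixed before unblinding. Otherwise leave site out of the primary model.

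The cost is a few lines of text and one regression per endpoint. No new data are needed, and one degree of freedom is spent on baseline.

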9.4.1 SAFETY ANALYSES

Adverse events will be recorded. The number and percent of patient incidence of all AEs, AEs related to study drug, serious adverse events (SAEs), SAEs related to study drug, deaths during the study, and study drug discontinuations due to an AE or study withdrawals due to an AE will be calculated. Patient listings will be recorded for SAEs, deaths, and AEs leading to study drug discontinuation, or study withdrawals. Patients will be followed for 30 days after completion or study discontinuation for the occurrence of any SAE.

9.4.2 BASELINE DESCRIPTIVE STATISTICS

Demographic variables will include age, race, ethnicity, sex, height, and weight. Participant demographics will be summarized with descriptive statistics, as appropriate. Clinical characteristics will also be summarized.

10 SUPPORTING DOCUMENTATION AND OPERATIONAL CONSIDERATIONS

10.1 REGULATORY, ETHICAL, AND STUDY OVERSIGHT CONSIDERATIONS

This study will be conducted in accordance with Good Clinical Practice (GCP), as defined by the International Conference on Harmonization (ICH) and in accordance with the ethical principles underlying European Union Directive 2001/20/EC and the United States Code of Federal Regulations, Title 21, Part 50 (21CFR50).

The study will be conducted in compliance with the protocol. The protocol and any amendments and the participant informed consent and assent forms (if applicable) will receive Institutional

Review Board approval prior to initiation of the study.

Study personnel involved in conducting this study will be qualified by education, training, and experience to perform their respective task(s).

10.1.1 INFORMED CONSENT PROCESS

Investigators will ensure that participants, or, in those situations where consent cannot be given by participants, their legally acceptable representatives, are clearly and fully informed about the purpose, potential risks, and other critical issues regarding the study.

10.1.1.1 CONSENT PROCEDURES AND DOCUMENTATION

The PPF for parent(s)/legally designated representative and the Assent Form for developmentally capable participants will be provided in English. Distinct assent forms are provided per age categories (7-11, 12-17). Site personnel authorized to participate in the consent/ assent process and/or to obtain consent/assent from the parent(s)/legally designated representative and participant will be listed on the Delegation of Authority form. The consent process will take place in a quiet, private exam room or over the phone. If over the phone, a copy of the consent and assent, if applicable, will be mailed or emailed to the parent or legal guardian prior to the phone consent conversation. Parent(s)/legally designated representatives and participants will be given ample time to review the consent forms and ask questions. A study physician will be available to answer medical questions or questions regarding alternative therapies.

The parent(s)/legally designated representative and/or participant must sign and personally date (if the first study-mandated procedure is to be performed on the same day informed consent is obtained) the PPF before any study-related procedures (i.e., any procedures required by the protocol) begin. The PPF/Assent must also be signed and personally dated (if the first study-mandated procedure is to be performed on the same day informed consent is obtained) by the authorized site personnel listed on the Delegation of Authority form.

If consented via phone, parents and participants will mail the signed consent and assent forms to study staff. The individual responsible for consenting the parent and participant will then sign the form(s) and mail a copy of the signed forms back to the parent. If consented in person, a copy of the signed and dated PPF/Assent will be given to the parent(s)/legally designated representative at the time of the visit; the original will be filed in the site documentation. The informed consent process as well as the assent process will be fully documented in the participant's medical records. This will include the study title, the participant number, the date and, if applicable, time when the participant's parent(s)/legally designated representative was first introduced to the study, the date of consent, who participated in the consent discussion, who consented the participant's parent(s)/legally designated representative, and any additional person present during the consent process (e.g., participant, any other family member), and a statement that a copy of the signed PPF/Assent has been given to the participant's parent(s)/legally designated representative.

10.1.2 STUDY DISCONTINUATION AND CLOSURE

The study starts with the first patient recruited (i.e., Informed Consent Form [ICF] signed) and ends with the last visit/contact of the last participant. The study is considered completed when the last participant completes the study (i.e. last final follow-up contact).

10.1.3 CONFIDENTIALITY AND PRIVACY

All efforts will be made to protect the privacy of individuals in this study. All health information and study data will be entered into REDCap. REDCap is a secure online database management tool. Only authorized users will have access to the study in REDCap. All authorized users will sign a REDCap user agreement. Data will be secured with a backup client.

